## 8.3. Screen Failures

Any subject who provides written informed consent/assent and is ultimately not infused for whatever reason will be classified as a screen failure. All subjects, including screen failures, must be accounted for in the clinical database.
# 8.4. Subject Withdrawal Criteria

Every effort will be made to have each subject complete all elements of the trial. If a subject has started at least one IP infusion and withdraws prior to trial completion, all attempts must be made to perform the trial assessments indicated for the Month 6 visit (i.e., final comprehensive visit).

Criteria for withdrawal from trial participation include the following reasons:

- A subject may withdraw his consent at any time without prejudice to his care.
- At the discretion of the Investigator, the subject may be withdrawn from the trial for lack of adherence to the investigational plan.
- A subject may be withdrawn from the trial for an acute reaction to CAP-1002 or other safety issue that prevents repeat infusions. In this instance, the subject should be followed on trial for at least 3 months after the last CAP-1002 infusion and then complete a final comprehensive visit.

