Trial visits at the investigative site will occur at Months 3 and 6 ( $\pm$ 14 days, respectively). Subjects will complete safety and efficacy assessments prior to CAP-1002 administration at the Month 3 trial visit.

The *primary safety endpoints* include the incidence of the following from baseline through the 6-month timepoint:

- Acute respiratory decompensation within 2 hours following IP administration
- Hypersensitivity reaction
  - Hypersensitivity reaction is defined as a clinical syndrome including, but not limited to, fever, leukocytosis, or rash with onset  $\leq 2$  hours post infusion and lasting < 24 hours, in the absence of clinical signs of concomitant infection.
- All-cause mortality
- Serious adverse events
- Treatment-emergent adverse events related to IP or administration procedure
- Immune sensitization syndrome
  - Immune sensitization syndrome shall be defined as: (a) clinical signs and symptoms consistent with systemic inflammation (e.g., fever, leukocytosis, rash, or arthralgia) with onset ≥ 24 hours post infusion and the absence of clinical signs of concomitant infection, AND (b) elevation of anti-human leukocyte antigen (HLA) antibodies against the donor cells (i.e., DSAs), detected ≤ 30 days following onset of syndrome, of (i) ≥ 2000 mean fluorescent intensity (MFI) if baseline MFI ≤ 1000, or (ii) ≥ 2 times baseline otherwise

The *exploratory endpoints* include the change from baseline to each assessment timepoint for the following assessments:

- All subjects
  - Mid-level (elbow) dimension of the Performance of Upper Limb (PUL) 1.2
  - Mid- and distal-level (elbow) dimension of the PUL 1.2
  - High-level (shoulder) dimension of the PUL 1.2
  - Left ventricular structure and function as assessed by cardiac MRI including regional systolic left ventricular wall thickening ejection fraction, end-diastolic volume, endsystolic volume, stroke volume, regional wall thickness, and circumferential strain
  - Slow vital capacity (SVC), forced expiratory volume in one second (FEV1), forced vital capacity (FVC), peak expiratory flow (PEF), maximum inspiratory pressure (MIP), maximum expiratory pressure (MEP), peak cough flow (PCF), and inspiratory flow reserve (IFR)
- Ambulatory subjects only

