#### Investigational Product, Dosage and Mode of Administration:

**Duration of Treatment:** CAP-1002 is administered as a single intravenous infusion on Day 1 and at Month 3 for a total of 2 administrations.

Duration of Trial: All subjects will be followed for 6 months post Day 1 infusion.

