#### 13.2.4. Reporting Adverse Events

All adverse events are collected from the time of signing informed consent for trial participation until completion of 6 months or early termination, whichever occurs first. All AEs occurring after the initiation of the IV catheter placement for the initial dose of CAP-1002 will be considered treatment emergent. Any ongoing adverse event that has not been resolved at the time of trial completion or early termination for a subject will be marked as ongoing on the adverse event case report form (CRF).

All AEs will be entered into the electronic data capture (EDC) system by trained site personnel at the investigative site.

Expected and unexpected SAEs must be reported to Capricor and entered into the EDC system within 24 hours of discovery of the event. For events that do not have complete information available at the time of initial report, the investigative site will submit all available information at the time of the submission. All SAE Report Forms must be signed by an Investigator and submitted with available source documentation. All source documentation must be de-identified prior to submission.

ALL SAES and subsequent follow-up information must be reported to Capricor, or designee, via email or fax as outlined in the Manual of Procedures and Safety Plan.

All SAEs must be reported to the respective IRB in accordance with the investigative site's policies. Copies of the submission will be collected by Capricor.

All SAEs will be reported to the DSMB at least semi-annually, or more frequently at the discretion of the Medical Monitor.

Capricor will promptly upon discovery, report serious and unexpected adverse events for which there is a reasonable possibility that the investigative therapy (i.e. administration product and/or investigative product) caused the events, to the Food and Drug Administration (FDA) in accordance with 21 CFR 312.32 regulations and ICG E2A guidelines.

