#### 13.2.6. Adverse Event Follow-up

All AEs are followed by the investigative site until an outcome is known or the subject's participation in the trial concludes at either 6 months or early termination, whichever occurs first.

The investigative site is expected to review all ongoing AEs at each visit. AEs are followed until resolution or until no further changes in the event are expected (i.e., the point at which a subject experiencing an AE is treated successfully and stabilized even though he may continue to experience lingering sequelae that may never resolve), or it is agreed that further follow-up of the event is not warranted (e.g., non-serious, IP unrelated, ongoing at final visit). See Section 13.2.3 for reporting ongoing AEs at the end of trial participation.

For SAEs that were incomplete or ongoing at the time of initial submission, the investigative site is required to submit follow-up SAE Report Forms when event information is available to the research site personnel and/or an outcome is known.

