## **APPENDIX B: SCHEDULE OF ASSESSMENTS**

Procedure / Event 	Screening	Day 1 (Infusion #1)	Post-Infusion #1 Safety Monitoring	Week 4	Month 3 (Infusion #2)	Post-Infusion #2 Safety Monitoring	Month 4	Month 6 / Early Termination 
Trial Day (Visit Window)	≤ 30 days prior to Day 1		14 days (±3) after Infusion #1	30 days (± 7)	90 days (±14)	14 days (±3) after Infusion #2	120 days (± 7)	180 (±14)
Informed Consent / Assent	х							
Eligibility Assessment	Х	Х						
Prior & Concomitant Meds	Х	Х	х		Х	х		Х
Medical History	Х							
Medical Status Questionnaire		х			х			х
Adverse Events	Х	Х	Х		Х	Х		Х
CAP-1002 IV Infusion 		Х			Х			
Post-Infusion Safety Call 4			Х			х		
Vital Signs		Х			Х			х
Height / Ulna Length 		Х			Х			Х
Weight		Х			Х			х
Physical Examination		Х			Х			х
12-Lead ECG		Х			х			х
Serum Chemistry 	Х	Х		Х	Х		Х	Х
Hematology 		Х		Х	Х		Х	Х
Cardiac Enzymes 		Х			Х			х
HLA Typing 		Х						

CONFIDENTIAL

Procedure / Event 	Screening	Day 1 (Infusion #1)	Post-Infusion #1 Safety Monitoring	Week 4	Month 3 (Infusion #2)	Post-Infusion #2 Safety Monitoring	Month 4	Month 6 / Early Termination 
Trial Day (Visit Window)	≤ 30 days prior to Day 1		14 days (±3) after Infusion #1	30 days (± 7)	90 days (±14)	14 days (±3) after Infusion #2	120 days (± 7)	180 (±14)
Donor-Specific Antibodies 		х		х	х		х	х
PUL 1.2		Х			Х			х
6-Minute Walk Test 		Х			Х			Х
Pulmonary Function Testing 		х			х			х
Cardiac MRI 	Х							Х

 Sites will complete assessments in the following sequence: 1) safety and other trial assessments, excluding blood collection (e.g., vital signs, height, weight, 12- lead electrocardiogram [ECG], etc.), 2) pulmonary function testing (PFT), 4) PUL 1.2, 5) 6MWT, 6) blood collection, 7) cardiac MRI (if applicable), and 8) CAP-1002 Infusion (if applicable). All efforts must be made for the same clinical evaluator to complete assessments for the same subject at the same time of day throughout the trial (preferably in the morning).

 All attempts must be made to perform the trial assessments indicated for the Month 6 visit (i.e., final comprehensive visit) for subjects that decide to early terminate early from the trial after starting at least one CAP-1002 infusion.

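### For a subject stopped for safety after infusion 1, the protocol lets follow-up end near Day 90, although the primary safety endpoints run to 6 months

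*Protocol*

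**What the plan says.** **Endpoint window.** The primary safety endpoints are incidences "from baseline through the 6-month timepoint" (protocol synopsis; same window in protocol 7.2.1 and SAP 2.2.1).

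**Planned follow-up.** The synopsis, under Duration of Trial, states without exception: "All subjects will be followed for 6 months post Day 1 infusion".

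**Stops for safety.** Protocol 8.4 covers a subject with an "acute reaction to CAP-1002 or other safety issue that prevents repeat infusions". It says that he "should be followed on trial for at least 3 months after the last CAP-1002 infusion and then complete a final comprehensive visit". The section treats this as withdrawal from the trial.

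**End of event collection.** Protocol 13.2.4 collects adverse events "until completion of 6 months or early termination, whichever occurs first". Protocol 13.2.6 ends follow-up of events when an outcome is known or when "the subject's participation in the trial concludes at either 6 months or early termination, whichever occurs first".

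**Analysis.** Under SAP 4.4 the Safety population is everyone who received any investigational product, and SAP 7 uses it for the safety summaries. SAP 4 bases percentages on subjects with available data. SAP 4, 7 and 7.1 give no person-time, censoring or time-at-risk rule. Protocol 14.6.2 plans no imputation and makes sensitivity analyses optional.

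**Visit labels.** The schedule (protocol Table 3, SAP Appendix B) has one column headed "Month 6 / Early Termination". SAP 6.1 to 6.4 do not say how early-termination efficacy values are labelled in the summaries.

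**The concern.** A site can comply with sections 8.4, 13.2.4 and 13.2.6 and still not deliver the 6 months of follow-up that the synopsis promises and the endpoints require. The shortening is triggered by a safety outcome, so it is not random with respect to what is being measured.

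The SAP does not offset this. A subject with three months of adverse-event data has data, so nothing removes him from the denominator, and his unobserved Months 3 to 6 are counted as if nothing happened. The endpoints exposed are:

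- all-cause mortality;
- serious adverse events;
- immune sensitization syndrome, whose definition has a minimum onset of 24 hours but no upper limit;
- related treatment-emergent events, if the stop was not itself for a related event.

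The second issue is labelling. The final comprehensive visit consists of the Month 6 assessments and shares that column. Values taken about three months after a single infusion could therefore be averaged with values taken at six months after two. Cardiac MRI is the clearest case: protocol 11.6 schedules it only at Screening and at Month 6 or early termination, so the early scan would be that subject's only post-baseline scan.

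**Working it through.** The plan has no power calculation or computed figure on this point to reproduce. The check is schedule arithmetic, followed by an illustration.

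**Inputs.** Infusions on Day 1 and at Month 3 (synopsis). Month 3 is 90 days ±14 and Month 6 is 180 days ±14 (Table 3). Minimum follow-up after a safety stop is 3 months from the last infusion (8.4), taken as 90 days as in the schedule. Up to 10 subjects (protocol 7.3). Days are counted from the first infusion.

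**Step 1: earliest end of follow-up = day of last infusion + 90.** The Month 6 window is Day 166 to Day 194.

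| Last infusion | Earliest end | Short of Day 180 | Short of Day 166 |
|---|---|---|---|
| Infusion 1 (0) | 90 | 90 | 76 |
| Infusion 2, Day 76 | 166 | 14 | 0 |
| Infusion 2, Day 90 | 180 | 0 | 0 |
| Infusion 2, Day 104 | 194 | 0 | 0 |

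A stop at infusion 1 may leave 90/180 = 50% of the window observed. After infusion 2 the minimum falls exactly on the Month 6 window, so nothing is lost beyond the ordinary visit tolerance.

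**Step 2: which endpoints can be lost.** Acute respiratory decompensation and hypersensitivity reaction both have a 2-hour limit after infusion, so a stop after infusion 1 hides neither. If the reaction that caused the stop was judged related, the subject already counts in the overall related-event incidence, because SAP 7.1 counts subjects once. If it was serious, he already counts for serious events.

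**Step 3: illustration of unobserved risk.** The documents give no later event risk for such a subject. Assume a 6-month risk p for an endpoint not yet met and a constant hazard. The risk seen in the first half is 1 − (1 − p)^0.5. The expected understatement of a 10-subject incidence, per truncated subject, is (p − seen)/10.

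| Assumed p | Seen by Day 90 | Share of p seen | Expected understatement (percentage points) |
|---|---|---|---|
| 5% | 2.5% | 51% | 0.25 |
| 10% | 5.1% | 51% | 0.49 |
| 20% | 10.6% | 53% | 0.94 |
| 30% | 16.3% | 54% | 1.37 |
| 50% | 29.3% | 59% | 2.07 |

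**Step 4: one event actually missed.** The reported incidence moves from 1/10 (exact 95% interval 0.3% to 44.5%) to 0/10 (0% to 30.8%), a change of 10 percentage points.

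**Step 5: observation time.** Each truncated subject costs 90 of 10 × 180 = 1,800 planned person-days, or 5%.

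**The case against.** **The 3 months is a floor.** Section 8.4 says at least 3 months, and it opens by asking for every effort to have subjects complete the trial. This stands: the text permits truncation and does not require it. A reader might infer that every subject stopped for a reaction is cut short; the documents do not say so, and after infusion 2 it cannot happen beyond the visit tolerance. What remains is that completeness of a primary endpoint depends on site discretion.

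**Observation per infusion is equal.** Three months after the last infusion is what a completer has after infusion 2, so 8.4 is coherent as a post-dose rule. This also stands. The shortfall is against the 6-month window, which is the window the endpoints use.

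**The risk model is unsupported.** A constant hazard makes Months 3 to 6 without a second infusion as risky as the months after an infusion, and nothing in the documents supports that. Protocol 13.2.1.3 reports no significant immune events linked to the product to date. The table is therefore an illustration, and the 10 points is the result only if an event is actually missed.

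**These may not be the highest-risk subjects.** It is tempting to call them that, but the documents give no later risk by reaction status.

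**Pooling into Month 6 is not stated.** Correct. A shared column lists procedures, and the nominal visit in SAP 4 concerns the sorting of listings. The SAP allows pooling by silence. It defines an end-of-study value for laboratory tests, vital signs and ECG (SAP 7.3 to 7.5), but gives no equivalent for efficacy.

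**Truncated subjects would be visible.** SAP 5.13 and 5.14 report visit completion, discontinuation and reasons. With 10 subjects a reader could work it out, but not from the endpoint table itself.

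**Conclusion.** The protocol contradicts itself on how long a subject stopped for safety after infusion 1 is followed, and the reading in 8.4, 13.2.4 and 13.2.6 leaves the 6-month incidence incomplete for him. At the minimum, 50% of the window is observed.

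The effect is confined to endpoints he has not already met: death, serious events, late-onset immune sensitization, and related events if the stop was not for one. It does not extend to the two 2-hour endpoints or to stops at infusion 2.

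Under the constant-hazard assumption, with 6-month risks of 5% to 50%, the expected understatement is about 0.2 to 2.1 percentage points per truncated subject in a 10-subject incidence; one event actually missed is 10 points. The number of such subjects is unknown and may be zero.

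The trial is descriptive with no formal hypotheses (protocol 14.1), so no test is compromised. The change is still worth making, because these are the primary safety endpoints and the correction is mostly wording.

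**What to change.** 1. **Protocol.** Reconcile the synopsis (Duration of Trial) with sections 8.4, 13.2.4 and 13.2.6, so that the period of safety-event collection matches the 6-month endpoint window for subjects who receive no further infusions and have not withdrawn consent. This concerns data collection only, not whether infusions stop.
2. **SAP.** State that early-termination assessments are summarised at the scheduled visit matching their actual study day, or in a separate row, and not as Month 6. The early-termination cardiac MRI needs its own row if it falls near Day 90, because no Month 3 scan is scheduled.
3. **SAP.** Show the number of subjects with complete 6-month follow-up beside each primary safety endpoint.

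The cost is wording in both documents and one extra column in the safety summary. The downside is a small extra follow-up burden for the few subjects affected.

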# 9. TREATMENT OF SUBJECTS

# 9.1. Description of Investigational Product

# CAP-1002 consists of allogeneic cardiosphere-derived cells or CDCs in a cryogenic cell preservation solution.

# 9.2. Treatment Compliance

CAP-1002 will be administered in a licensed infusion center, or other appropriate unit according to a site's institutional standards, by appropriately trained medical personnel who will document the actual volume administered at each infusion.

# 10. INVESTIGATIONAL PRODUCT MATERIALS AND MANAGEMENT

Detailed investigational product information can be found in the Investigator's Brochure (IB) and the Investigational Product Manual. Below and elsewhere in the protocol, reference is made to an investigational pharmacist which is typically a person licensed to dispense prescription medication usually within a special unit of the institutional pharmacy that handles all investigational products. CAP-1002 is a cell-based investigational product, therefore the chain of custody and responsibility for preparation of the investigational product may reside within another institutional department or unit, such as a center for cellular therapy or human cellular therapy laboratory or similar name, in which case "investigational pharmacy" shall mean the special center, laboratory or unit within the institution designated to handle all cell-based therapies and "investigational pharmacist or other designee" shall mean the person delegated by the Principal Investigator as having the role in receiving, storing and preparing CAP-1002 who may not be a licensed pharmacist.

# 10.2. Master Cell Banks / CDC Donor

CDCs will be grown from a donor unrelated to the recipients. Subjects will receive CDCs produced from the same Master Cell Bank (MCB) without regard to pre-existing DSA levels and based on lot available inventory. A subject's anti-HLA antibody levels specific to the CDC

donor used for CAP-1002 production (i.e., DSA) will be assessed at screening and throughout the course of the trial per Section 13.1.5.

Page 41 of 75 Capricor, Inc. - Company Confidential

# 10.6. Administration

CAP-1002 will be administered in an outpatient setting at the investigative site on Day 1 and Months 3. Subjects must complete all other trial assessments prior to CAP-1002 infusion, excluding those related to the CAP-1002 infusion (e.g., post-infusion monitoring). CAP-1002 will be administered as an IV infusion using a commercially available syringe pump approved for human use at an infusion rate of 4 mL/min.

# 10.7. Post-Infusion Monitoring

Subjects will remain in the outpatient setting for at least 2 hours post infusion for observation. Investigative sites will observe their local institutional policies for post parenteral infusion monitoring. The subject's pulse oximetry (SpO2) will be monitored for at least 30 minutes post infusion. A site Investigator will assess the subject for adverse events and approve his discharge the same day if medically cleared.

# 10.8. 14-Day Post-Infusion Monitoring

Subjects will complete a safety, follow-up phone call 14 days (±3 days) after each CAP-1002 infusion to document subject-reported AEs and new concomitant medications.

If clinically indicated, an unscheduled in-person visit will be performed at the investigative site with targeted assessments based on presentation of signs and symptoms of the subject.

# 10.9. Accountability

Good Clinical Practice (GCP) and FDA regulations assign responsibility for investigational product accountability at the trial site with the Principal Investigator. The Investigator may elect to delegate this responsibility to the investigational pharmacist, or other designee, who is under the supervision of the Investigator.

The responsible person must maintain a record of CAP-1002 received, prepared, administered and returned/destroyed. Therefore, CAP-1002 accountability must be maintained throughout the trial to show clear product traceability at all times. Details regarding CAP-1002 accountability will include dates, quantities, batch/serial numbers, expiration dates if applicable, storage conditions and the unique code assigned to the CAP-1002 and subjects. CAP-1002 accountability must adequately document that the subjects were provided the correct vial and

reconcile all CAP-1002 received from Capricor's drug depot. Further information on CAP-1002 accountability is found in the Investigational Product Manual.

# 10.10. Handling and Disposal

All CAP-1002 materials will be disposed following each infusion. Site personnel will follow institutional policies on the proper disposal of containers and disposables coming into contact with the CAP-1002. Generally, disposal like other biohazard red-bag trash that is ultimately incinerated should be sufficient to meet local institutional policies and any other regulations or laws.

# **11. ASSESSMENT OF EFFICACY**

Assessments to evaluate efficacy will be performed at trial visits as indicated in Table 3.

#### **11.1.** Sequence of Assessments

Subjects will complete assessments in the following sequence and prior to IP infusion (if applicable):

- Safety and other trial assessments, excluding blood and urine collections (e.g., vital signs, height, weight, 12-lead ECG, physical exam etc.)
- Pulmonary function testing
- PUL 1.2
- 6MWT
- Blood and urine collections
- Cardiac MRI

# At the Month 3 follow-up visit, subjects will complete the efficacy assessments designated for that visit prior to CAP-1002 administration.

#### 11.2. Efficacy Assessment Training

Site personnel must complete trial-specific training prior to conducting efficacy assessments for the trial. Standardization and consistency are essential. All efforts must be made to have the same clinical evaluators conduct the PFT, PUL, and 6MWT assessments and the same imaging technologist conduct the cardiac MRI for a subject throughout the duration of the trial. Additional details regarding training requirements can be found in Section 17.1 and the trial's Manual of Procedures (MOP).

